2.5.6 Supplementary analyses

Subgroup analyses

Subgroup analyses to assess the homogeneity of the treatment effect across demographic and baseline characteristics will be performed. The subgroup variables are defined in [Table 2-1](#).

The subgroup analyses will be based on the multiply imputed datasets created for the primary analysis. Within each subgroup, the same ANCOVA model as described in [Section 2.5.2](#) will be used. For the analysis of subgroups which are also stratification factors, the corresponding stratification factor term will be removed from the model. The least squares means for the difference between inclisiran and two comparators and corresponding unadjusted two-sided confidence intervals (CI) will be provided separately. The unadjusted p-value for testing the individual hypothesis will also be provided. No adjustment for multiple comparisons will be made. Forest plot will be provided for subgroup analyses. If the model did not converge for a subgroup, the results for that subgroup will be left blank or indicated as not estimable.

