3.1 Primary endpoints

The sample size calculation was based on a two sample t-test for the hypothesis that inclisiran is superior to either placebo or ezetimibe in terms of mean percentage change from baseline to Day 150 in LDL-C, at a one-sided significance level of 0.0125 (assuming a more conservative Bonferroni alpha split between the two primary hypotheses).

The sample size of 280 completers in total (with randomization ratio of 2:1:1 to inclisiran, placebo, and ezetimibe arms) will provide at least 99% power to detect a 40% difference between inclisiran and placebo or a 20% difference between inclisiran and ezetimibe at significance level of 0.0125 (one-sided test) assuming 30% for the standard deviation. Adjusted for 6% potential dropouts, approximately 300 participants in total will be randomized with a 2:1:1 ratio, i.e., 150 participants in the inclisiran arm, and 75 participants in both the placebo and ezetimibe arm.

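### The subgroup analyses aim to assess homogeneity, but the plan never estimates or tests how the treatment effect differs between subgroup levels

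*SAP*

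**What the plan says.** SAP 2.5.6 (Subgroup analyses) gives the purpose: "Subgroup analyses to assess the homogeneity of the treatment effect across demographic and baseline characteristics will be performed". The method is stratified: "Within each subgroup, the same ANCOVA model as described in" Section 2.5.2 is fitted, using the imputed datasets from the primary analysis. The output is LS-mean differences against each comparator, unadjusted two-sided confidence intervals, p-values and a forest plot. On the p-values it says: "The unadjusted p-value for testing the individual hypothesis will also be provided. No adjustment for multiple comparisons will be made". A level is left blank or marked not estimable only if its model fails to converge; no minimum size is set.

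SAP Table 2-1 marks nine factors for efficacy: age, sex, race, region, hypertension, ASCVD risk score, screening LDL-C, PCSK9 and Lp(a). SAP 2.2.1 describes the purpose more loosely, as exploring whether subgroups are consistent with the overall population. Protocol 12.4.6 leaves the subgroup definitions to the SAP. Neither document plans an estimate or test of the difference in effect between levels. The SAP document history records that amendment 1 moved from interaction-term models to within-subgroup models. That is background only; the point rests on the current text.

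**The concern.** Homogeneity is a question about the difference between levels: is the effect in women the same as in men, or in one region the same as in another? A p-value from one level answers another question, namely whether the effect in that level is zero. Comparing two such p-values is not a test of their difference. A small level can miss significance next to a large one although the true effects are equal, and two significant levels can have truly different effects that nothing in the output quantifies.

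What is at stake is how the subgroup tables are read. A non-significant level against ezetimibe could be reported as a group in which inclisiran is no better, and the plan supplies no figure with which to check that claim.

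**Working it through.** **Inputs.** From SAP 3.1: "at least 99% power to detect a 40% difference between inclisiran and placebo or a 20% difference between inclisiran and ezetimibe", "assuming 30% for the standard deviation", and a test "at a one-sided significance level of 0.0125". There are 280 completers at 2:1:1, which is 140/70/70; and "Adjusted for 6% potential dropouts, approximately 300 participants in total will be randomized with a 2:1:1 ratio", which is 150/75/75. Assumed, because the documents do not give them: the share f of participants in a level (the same in every arm), and reading each subgroup p-value at two-sided 0.05.

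**The plan's own figure.** SE = 30·√(1/140 + 1/70) = 4.39. Noncentrality versus ezetimibe = 20/4.39 = 4.55 on 208 df. Power at one-sided 0.0125 is 98.9%, which is the stated 99% after rounding. Versus placebo it exceeds 99.99%. 280/0.94 = 298, about 300. The design figures reproduce.

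**Number of p-values.** Seven factors have two levels and two (race, region) have three: 7×2 + 2×3 = 20 levels. With two comparators that is 40 unadjusted p-values per estimand.

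**Chance discordance when the effect is homogeneous.** Power in a level comes from the noncentral t with noncentrality δ/(30·√(1/n₁ + 1/n₂)). If the two levels have powers p₁ and p₂, the chance that exactly one is significant is p₁(1−p₂) + p₂(1−p₁).

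Example, 10/90 versus ezetimibe on completers:
- Small level, 14 vs 7: SE = 30·√(1/14 + 1/7) = 13.9, noncentrality 1.44, power 0.277.
- Large level, 126 vs 63: SE = 4.63, noncentrality 4.32, power 0.990.
- Discordance = 0.277×0.010 + 0.990×0.723 = 0.72.

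| Split (assumed) | Ezetimibe, 140/70 | Ezetimibe, 150/75 | Placebo, 140/70 | Placebo, 150/75 |
|---|---|---|---|---|
| 50/50 | 20% | 16% | 0% | 0% |
| 20/80 | 49% | 46% | 2.2% | 1.5% |
| 10/90 | 72% | 70% | 22% | 19% |

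Age, PCSK9 and Lp(a) are split at the median, so the first row applies to them by construction.

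**All 20 levels together.** A simulation (1000 runs per scenario, Welch tests, no covariates, independent factors, identical true effects) gave the chance of at least one non-significant level. Versus ezetimibe it was 78% with even splits and 95% with skewed splits (smallest level 10%). Versus placebo it was 0.7% and 44%.

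**What a between-level comparison could deliver.** On completers, SE of the difference in effect = 30·√(1/(140f) + 1/(70f) + 1/(140(1−f)) + 1/(70(1−f))).

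| Split | SE (points) | Difference detectable with 80% power (2.80×SE) |
|---|---|---|
| 50/50 | 8.8 | 24.6 |
| 20/80 | 11.0 | 30.8 |
| 10/90 | 14.6 | 41.0 |

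Power for a true 10-point difference at 50/50 is about 21%. Nine factors × two comparators = 18 tests per estimand. If they are independent and effects are homogeneous, the chance of at least one p<0.05 is 1 − 0.95¹⁸ = 60%.

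**Reference distribution.** With variances estimated separately in small arms, a plain z-test rejects too often. Simulated type I error at nominal 5% (complete data, no covariates, equal true SDs) is about 6.4–6.6% with 15 vs 8 in the small level of a 10/90 split, and about 8.6% with 8 vs 4 in a 5/95 split.

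**The case against.** The strongest defence is that estimates with confidence intervals on a forest plot are an accepted way to inspect consistency, and SAP 2.2.1 asks for little more than that. This stands in part: the plan answers its question informally. It does not stand as a full answer, because SAP 2.5.6 names homogeneity and a reader must still judge the size and precision of each difference by eye.

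The second defence is that discordance arises from small numbers and many levels, not from the absence of a test. That is correct. A reader might infer that adding a heterogeneity test would stop small subgroups looking different by chance. It would not: it would measure the difference validly, with low power and its own false positives.

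Third, the move to within-subgroup models was made before database lock and the protocol left the method to the SAP. That also stands, and the fix below does not require reversing it.

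Finally, versus placebo the 40-point effect protects all but very small levels. This stands too and limits the point mainly to ezetimibe.

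**Conclusion.** The point holds in a limited form. The plan states a homogeneity aim and supplies only within-level results, so the between-level difference is neither estimated nor tested. Versus ezetimibe, a misleading significant/non-significant contrast would appear roughly one time in five or six at an even split, about half the time at 20/80 and about seven times in ten at 10/90, even with identical true effects. Versus placebo the figure is negligible down to 20/80 and about one in five at 10/90.

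These figures rest on the design effects and SD, on assumed subgroup shares equal across arms, on two-sided 0.05, and on t-tests without covariates or imputation. Covariate adjustment, or a true SD other than 30, would shift them.

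A reader might infer that the subgroup plan weakens the trial's error control or its main result. The documents do not support that: these analyses are supplementary, openly unadjusted and outside the multiple comparison procedure of SAP Appendix 5.4. The change is worth making because it is cheap, not because the trial depends on it.

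**What to change.** In SAP 2.5.6:

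1. Keep the within-subgroup ANCOVA models, LS-mean differences, confidence intervals and forest plot.
2. Drop the within-subgroup p-values.
3. For each factor and comparator, add the between-level difference in treatment effect with its confidence interval and a heterogeneity p-value (a joint test for race and region, which have three levels). Form the contrast in each imputed dataset, then combine by Rubin's method, so that any covariance between levels induced by the imputation is carried through.
4. Use a small-sample t or F reference distribution instead of a plain z-test.
5. Label the results exploratory and unadjusted. State that power is low and that, over about 18 tests per estimand, at least one nominal p<0.05 has roughly a 60% chance under homogeneity if the tests are independent.

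The cost is some extra columns computed from models already being run; no interaction model is needed. If the sponsor prefers not to add the contrast, the lesser step is to describe the subgroup analyses as descriptive and remove the within-level p-values.

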2.6 Analysis supporting secondary objectives

2.6.1 Secondary endpoint(s)

There are seven secondary efficacy endpoints defined, and fourteen secondary hypotheses to be tested for these seven secondary endpoints in the comparison between inclisiran and each comparator (placebo or ezetimibe) respectively:

[figure not shown]
1. Percentage change in PCSK9 from baseline to Day 150
2. Absolute change in LDL-C from baseline to Day 150
3. Percentage change in non-HDL-C from baseline to Day 150
4. Percentage change in TC/HDL-C ratio from baseline to Day 150
5. Percentage change in Apo B from baseline to Day 150
6. Percentage change in Apo B/Apo A-1 ratio from baseline to Day 150
7. Percentage change in Lp (a) from baseline to Day 150

2.6.2 Statistical hypothesis, model, and method of analysis

For each of the secondary efficacy endpoints, the Treatment-policy Estimand and the Monotherapy Estimand will be defined in a similar way as for the primary endpoint. All secondary efficacy endpoints will be analyzed on FAS using the same ANCOVA model as for the primary efficacy endpoint as described in [Section 2.5.2](#). Lipoprotein (a) will be log-transformed before modeling. The model will include treatment, stratification factor, and baseline value as fixed effects, and assume unequal variances between treatment groups. The least squares means for the difference between inclisiran and two comparators and corresponding unadjusted two-sided CIs will be provided separately.

As stated in [Section 2.5.2](#), the two families of secondary hypotheses H_{IPk} and H_{IEk} ($k = 1, 2, \dots, 7$, following the order of the seven secondary endpoints as above) are included in the multiple testing procedure as presented in [Figure 2-1](#). The hierarchical testing procedure will be used to test the seven secondary hypotheses within each family of the secondary endpoints (H_{IPk} or H_{IEk}). If one secondary hypothesis in the comparison between inclisiran and placebo H_{IPk} is rejected, a fraction of its significance level will be passed to the next hierarchy of secondary hypotheses under the same treatment comparison, while the remaining alpha will be propagated to the primary hypothesis comparing inclisiran and ezetimibe, according to the pre-specified weights as indicated in the graph. If there is no next hierarchy of secondary hypotheses, then the whole alpha will be propagated to the primary hypothesis comparing inclisiran and ezetimibe. Vice versa for the alpha passing from H_{IEk} .

Figure 2-1 Testing procedure for primary and secondary endpoints

The intercurrent events and missing values will be handled following the same approach as described for the primary endpoint.

2.6.3 Handling of intercurrent events

Intercurrent events will be handled using the strategies described in [Section 2.5.3](#).

2.6.4 Handling of missing values not related to intercurrent event

Missing values not related to intercurrent events will be imputed as described in [Section 2.5.4](#).

2.7 Safety analyses

For all safety analyses, the SAF will be used. All tables and listings will be presented by treatment group and overall.

2.7.1 Adverse events (AEs)

The most recent version of MedDRA before DBL will be used for coding AEs. An AE will be counted as a treatment emergent AE (TEAE) if the AE started on or after Day 1 or the AE was present prior to Day 1 but increased in severity on or after Day 1. Since the investigators are required to enter any worsened AE as a separate record, implementation-wise an AE is a TEAE as long as its start date is on or after Day 1.

The following summaries will be presented for TEAEs using number and percentage of participants with the event:

- Overall Summary of TEAEs
- TEAEs by primary SOC and PT
- TEAEs by primary SOC
- TEAEs by PT
- TEAEs by primary SOC, PT, and maximum severity
- TEAEs possibly related to inclisiran/placebo by primary SOC and PT
- TEAEs possibly related to ezetimibe/placebo by primary SOC and PT
- TEAEs possibly related to inclisiran/placebo by PT
- TEAEs possibly related to ezetimibe/placebo by PT
- Treatment Emergent Serious AEs (TESAEs) by primary SOC and PT
- TESAEs by primary SOC
- TESAEs by PT
- TESAEs possibly related to inclisiran/placebo by primary SOC and PT
- TESAEs possibly related to ezetimibe/placebo by primary SOC and PT
- TEAEs leading to discontinuation of inclisiran/placebo by primary SOC and PT
- TEAEs leading to discontinuation of ezetimibe/placebo by primary SOC and PT
- TEAEs leading to discontinuation of inclisiran/placebo by PT
- TEAEs leading to discontinuation of ezetimibe/placebo by PT

- TEAEs with a fatal outcome by primary SOC and PT

If more than one event occurred with the same SOC/PT for the same participant, the participant will be counted only once for that SOC/PT.

Participant data listings will be presented for AEs with a fatal outcome, SAEs, AEs leading to discontinuation of inclisiran/placebo, and AEs leading to discontinuation of ezetimibe/placebo. Those listings will include all AEs in database, regardless of whether they are TEAE.

Additional Analysis of Adverse Events for ClinicalTrials.gov and EudraCT:

For the legal requirements of ClinicalTrials.gov and EudraCT, two required tables on treatment emergent adverse events which are not serious adverse events with an incidence greater than certain percentage in any treatment group and on treatment emergent serious adverse events and SAE suspected to be related to study treatment will be provided by SOC and PT on the SAF.

If for a same patient, several consecutive AEs (irrespective of study treatment causality, seriousness and severity) occurred with the same SOC and PT:

- a single occurrence will be counted if there is ≤ 1 day gap between the end date of the preceding AE and the start date of the consecutive AE
- more than one occurrence will be counted if there is > 1 day gap between the end date of the preceding AE and the start date of the consecutive AE

For occurrence, the presence of at least one SAE / SAE suspected to be related to study treatment / non-SAE has to be checked in a block e.g., among AEs in a ≤ 1 day gap block, if at least one SAE is occurring, then one occurrence is calculated for that SAE.

The number of deaths resulting from SAEs suspected to be related to study treatment and SAEs irrespective of study treatment relationship will be provided by SOC and PT.

2.7.1.1 Adverse events of special interest / grouping of AEs

Case Retrieval Strategy (CRS) will be used to determine the MedDRA search criteria to be used to identify adverse events of special interest (AESI). The number and percentage of participants with treatment emergent AESIs will be presented by treatment group, for each topic of AESI. The AESIs in this study are specified as follows:

- New Onset Diabetes Mellitus
- Hepatotoxicity

The following summary tables will be generated for the AESIs:

- Overall Summary of TEAEs
- TEAEs by PT
- TEAEs possibly related to inclisiran/placebo by PT

- TEAEs possibly related to ezetimibe/placebo by PT
- TEAEs by primary SOC, PT, and maximum severity
- TESAEs by PT
- TEAEs leading to discontinuation of inclisiran/placebo by PT
- TEAEs leading to discontinuation of ezetimibe/placebo by PT

Participant data listings will be provided for each topic of AESI, which will include all AEs in the database, regardless of whether they are TEAE. The CRS definitions for the AESIs will also be provided in a listing.

2.7.2 Deaths

As stated in [Section 2.7.1](#), TEAEs with fatal outcome will be summarized by primary SOC and PT. All deaths (regardless of treatment emergent or not) will be listed at the individual participant level as well.

2.7.3 Laboratory data

Observed value, absolute change, and percent change from baseline in safety laboratory parameters will be summarized descriptively at baseline (for observed value only) and at each post-baseline visit. eGFR will be summarized by categories (< 30 , ≥ 30 to < 60 , and ≥ 60 mL/min/1.73m 2) at baseline and at each post-baseline visit. For each parameter, only the visits at which the parameter is scheduled to be assessed per protocol will be presented for such visit-based summary.

For glucose, only measurements taken in a fasting state will be used. Baseline glucose is defined as the average of the last two non-missing fasting glucose values on or prior to Day 1. If only one non-missing fasting glucose value is available on or prior to Day 1, the available value will be used as baseline.

In addition, shift tables using the low, normal, or high classification based on the standard ranges for each laboratory parameter will be used to present incidence of transitions from baseline to the worst post-baseline value. For eGFR, HbA1c, and fasting glucose, the following ranges will be used:

- For eGFR, the categories will be Severe: < 30 mL/min/1.73m 2 ; Moderate: ≥ 30 to < 60 mL/min/1.73m 2 ; Normal or Mild: ≥ 60 mL/min/1.73m 2 .
- For HbA1c, the categories will be $< 5.7\%$, $\geq 5.7\%$ to $< 6.5\%$, and $\geq 6.5\%$.
- For fasting glucose, the categories will be < 100 mg/dL, ≥ 100 mg/dL to < 126 mg/dL, and ≥ 126 mg/dL

The number and percentage of participants with abnormalities in liver function tests (LFT) will also be summarized, according to the criteria defined in [Table 2-2](#).

The shift tables and the analyses of abnormalities in LFT will use all the available post-baseline laboratory assessments, including unscheduled visits and early exit.

Table 2-2 Notable liver function test criteria

Peak post-baseline value

ALT >3x ULN
ALT >5x ULN
ALT >10x ULN
ALT >20x ULN

AST >3x ULN
AST >5x ULN
AST >10x ULN
AST >20x ULN

ALT or AST >3x ULN
ALT or AST >5x ULN
ALT or AST >8x ULN
ALT or AST >10x ULN
ALT or AST >20x ULN

ALP > 2x ULN

Total bilirubin (BILI) >2x ULN
Total bilirubin (BILI) >3x ULN

Combined elevations post-baseline

For participants with AST and ALT =< ULN at baseline

Elevated ALT or AST (\$) & BILI >2x ULN
Elevated ALT or AST (\$) & BILI >2x ULN & ALP >=2x ULN
Elevated ALT or AST (\$) & BILI >2x ULN & ALP <2x ULN

For participants with ALT or AST > ULN at baseline

Elevated ALT or AST (*) & BILI (>2x Bsl and 2x ULN)
Elevated ALT or AST (*) & BILI (>2x Bsl and 2x ULN) & ALP >=2x ULN
Elevated ALT or AST (*) & BILI (>2x Bsl and 2x ULN) & ALP <2x ULN

ALT = alanine aminotransferase, AST = aspartate aminotransferase, ALP = alkaline phosphatase
Combined elevations based on the peak post-baseline values (considering all post-baseline data from scheduled, unscheduled and premature discontinuation visit) for each parameter for each participant.

* Elevated AST or ALT for participants with > ULN at baseline is defined as >3x Baseline or 8x ULN.

\$ Elevated AST or ALT for participants with =< ULN at baseline is defined as >3x ULN.

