**Table 8-1 Assessment Schedule**

Period	Screening	Baseline	Double-Blind Treatment Period 			Safety Follow-up
Visit Name	Screening 	V1	V2 	V3	V4 	V5 (EOS) 
Days	-14 to -1	1	30	90	150	180 +5
Informed consent	X					
Inclusion / Exclusion criteria	X	X				
Demography	X					
Smoking and alcohol history	X					
Medical history/current medical conditions	X					
Prior or concomitant medication 	X	X	X	X	X	X
Surgical/medical procedures 	X	X	X	X	X	X
Physical Examination	S	S		S		S
Body Height/Weight	X					
Vital Signs 	X	X	X	X	X	X
AEs/SAEs	X	X	X	X	X	X
Lifestyle instructions		S	S	S	S	S
Electrocardiogram (ECG)		X				
Follicle stimulating hormone (FSH)	X 					

Period	Screening	Baseline	Double-Blind Treatment Period 			Safety Follow-up
Visit Name	Screening 	V1	V2 	V3	V4 	V5 (EOS) 
Days	-14 to -1	1	30	90	150	180 +5
Pregnancy Test (serum) 	X					
Pregnancy Test (urine) 		X	X	X	X	X
Thyroid stimulating hormone 	X					
Fasting Lipid Profile 	X	X	X	X	X	
Fasting Lp(a) 		X			X	
PCSK9 		X	X	X	X	
Clinical Chemistry 	X					
Limited Chemistry 		X	X		X	X
Hematology 		X				X
HbA1c 	X					X
Urinalysis 	X					X
Coagulation Panel 		X				
Enter participant visit in IRT	X	X	X	X	X	X
Randomization		X				
Study drug administration - s.c. inclisiran/placebo		X 		X 		
Dispense ezetimibe/placebo		S	S	S		

Period	Screening	Baseline	Double-Blind Treatment Period 			Safety Follow-up
Visit Name	Screening 	V1	V2 	V3	V4 	V5 (EOS) 
Days	-14 to -1	1	30	90	150	180 +5
Control drug administration - p.o. ezetimibe/placebo		X 	X 	X 	X 	
Ezetimibe/placebo compliance			X 	X 	X 	
Disposition form	X				X 	X

 Assessment to be recorded in the clinical database or received electronically from a vendor

 Visit may be performed off-site in certain countries and sites as determined by protocol needs and based on national and local/site regulations.

 Visit 4 is also the EOT visit if the participant completes the study treatment as per protocol.

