## 9 Discontinuation and completion

### 9.1 Discontinuation from study treatment and from study

#### 9.1.1 Discontinuation from study treatment

Discontinuation of study treatment for a participant occurs when study treatment is permanently stopped for any reason (prior to the planned completion of study drug or control drug administration, if any) and can be initiated by either the participant or the investigator. If the participant permanently discontinues p.o. ezetimibe/placebo or s.c. inclisiran/placebo, then the participant's entire study treatment must be stopped. The treatment disposition CRF will be completed to reflect that the participant has permanently discontinued study treatment (both p.o. study drug and s.c. study drug).

The investigator must discontinue study treatment for a given participant if he/she believes that continuation would negatively impact the participant's well-being.

Discontinuation from study treatment is required under the following circumstances:

- Participant/guardian decision
- Pregnancy
- Use of prohibited treatment as per recommendations in the prohibited medication [Section 6.2.2](#)
- Any situation in which continued study participation might result in a safety risk to the participant
- Severe and persistent (> 14 days despite appropriate treatment) reactions at the injection site and any type of anaphylactic reactions
- Intolerable adverse events
- Unexplained increases in transaminases (ALT or AST) or total bilirubin confirmed by repeat test as follows:
  - ALT or AST > 8 x ULN
  - ALT or AST > 5 x ULN for more than 2 weeks
  - ALT or AST > 3 x ULN with simultaneous or subsequent elevation of total bilirubin > 2 x ULN
  - ALT or AST > 3 x ULN with the appearance of fatigue, nausea, vomiting, right upper quadrant pain or tenderness, fever, rash, and/or eosinophilia (> 5%)

The investigator should evaluate to see if other causes for the laboratory abnormalities are immediately apparent, such as obstructive gall bladder or bile duct disease, viral or alcoholic hepatitis, malignancy involving the liver, congestive hepatopathy, other hepatotoxins or heritable disorders. Please also refer to [Section 16.2 Appendix 2](#).

- Unexplained CK > 10 x ULN confirmed by repeat test when the CK elevation is associated with muscle pain, muscle tenderness and/or muscle weakness, or new onset renal dysfunction with no other alternative explanation
- Following emergency unblinding

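### SAP Table 2-2 splits combined liver elevations by peak ALP at any time, so a same-sample case with low ALP can be filed in the high-ALP row

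*SAP*

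**What the plan says.** SAP section 2.7.3 plans counts of participants with liver test abnormalities, defined in Table 2-2. The combined part has a parent row (elevated ALT or AST with raised bilirubin) and two complementary sub-rows by ALP. For participants with normal transaminases at baseline the sub-rows are "BILI >2x ULN & ALP >=2x ULN" and "BILI >2x ULN & ALP <2x ULN", each together with elevated ALT or AST. The threshold is given as "Elevated AST or ALT for participants with =< ULN at baseline is defined as >3x ULN". A parallel set of rows covers participants whose ALT or AST was raised at baseline.

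The footnote sets the rule for all these rows: "Combined elevations based on the peak post-baseline values", and continues "considering all post-baseline data from scheduled, unscheduled and premature discontinuation visit) for each parameter for each participant". The text above the table has the same scope: these analyses "will use all the available post-baseline laboratory assessments, including unscheduled visits and early exit". Nothing in the SAP adds a same-sample requirement, a time window or an order.

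Protocol section 9.1.1 does attach timing to a similar combination, as one of its criteria for stopping study treatment: "ALT or AST > 3 x ULN with simultaneous or subsequent elevation of total bilirubin > 2 x ULN".

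**The concern.** The rule is explicit, so it would be programmed as three separate maxima (ALT/AST, bilirubin, ALP), with the thresholds applied afterwards. The three values need not come from the same illness or the same month.

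The ALP split suffers most. Its purpose is to describe the pattern that accompanied the transaminase and bilirubin rise, and an ALP value from another time does not describe it. The protocol judges pattern by the R value (section 6.6.3.1), the ratio of ALT to ALP in multiples of ULN, and defines cholestasis partly by ALP above 2 x ULN. A participant moved between the ALP rows would therefore be read differently.

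Hepatotoxicity is one of two AESIs (SAP 2.7.1.1), and Table 2-2 is the planned laboratory-based count of combined elevations. With about 150 participants on inclisiran, one participant is 1/150 = 0.7% of the arm, so one misplaced case can change how a row reads.

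**Working it through.** The plan gives no figure to reproduce here. The check applies the footnote to constructed participants.

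**Inputs**
- Liver chemistry after baseline: limited panel at Days 30, 150 and 180, none at Day 90 (protocol Table 8-1).
- AST, ALT, ALP and total bilirubin are all on that panel (protocol Table 8-3).
- Windows: plus or minus 5 days at Days 30 and 150; EOS 30 to 35 days after the Day 150 visit (protocol section 8).

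**How far apart paired peaks can be (scheduled visits)**
- Day 30 to Day 150: 150 − 30 = 120 days nominal; 145 − 35 = 110 to 155 − 25 = 130 within windows.
- Day 30 to EOS: 180 − 30 = 150 days nominal; at most (155 + 35) − 25 = 165.

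**Rule applied to invented participants** (multiples of ULN, normal transaminases at baseline, values not shown unremarkable)

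| Case | Values | Peak rule (SAP) | Same-sample rule | Bilirubin at or after ALT |
|---|---|---|---|---|
| A | ALT 3.5 at Day 30; bilirubin 2.3 at Day 150 | Parent row, low ALP | Not counted | Met |
| B | Bilirubin 2.3 at Day 30; ALT 3.5 at Day 180 | Parent row, low ALP | Not counted | Not met |
| C | ALT 8, bilirubin 3, ALP 1.2 at Day 30; ALP alone 2.2 at Day 180 | Parent row, **high ALP** | Parent row, **low ALP** | Met |
| D | As C, without the late ALP rise | Parent row, low ALP | Parent row, low ALP | Met |

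Cases C and D have the same liver event at Day 30, where R = 8/1.2 = 6.7, hepatocellular by the protocol (R of 5 or more). They fall in different ALP rows only because of an isolated ALP value 150 days later. From the separate peaks in C, the ratio would be 8/2.2 = 3.6, in the protocol's mixed range.

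**Direction of the ALP error.** Peak ALP cannot be lower than ALP in the sample that meets the criteria. If that sample has ALP of at least 2 x ULN, so has the peak, and the row is unchanged. If it has ALP below 2 x ULN, the peak may still reach 2. Genuine concurrent cases can thus only leave the low-ALP row. Chance pairs such as A and B can enter it.

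**Direction of the parent-row error.** By the same argument for ALT/AST and bilirubin, every concurrent case is counted; the only possible error is an extra pair.

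**Expected chance pairs.** The documents give no liver event rates. Assume that 1 to 2% of participants have ALT/AST above 3 x ULN and 2 to 5% have bilirubin above 2 x ULN at some time, independently:
- low: 150 × 0.01 × 0.02 = 0.03 per 150 participants;
- high: 150 × 0.02 × 0.05 = 0.15 per 150 participants.

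The chance of at least one such pair in the inclisiran arm is about 1 − exp(−0.03) = 3% to 1 − exp(−0.15) = 14%. No rate for late ALP rises can be derived from the documents, so the frequency of case C is not estimated.

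**The case against.** The strongest reply is that a peak-based table is a deliberate, openly stated screen that errs toward over-flagging. A strict same-sample rule would be less sensitive: with scheduled chemistry at only three post-baseline visits, a bilirubin peak in a different sample from the ALT peak would be missed. This stands. It is a reason to add time-matched rows and not to replace the peak rows. It does not defend the ALP split, where the peak adds no sensitivity and only moves cases between rows.

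A second reply is that repeat testing fills the gaps. Protocol Table 16-2 asks for repeat panels at 48 to 72 hours after ALT/AST triggers, and Table 16-3 asks for weekly monitoring of isolated bilirubin elevations. Dated values would therefore exist for case review. That is true, but they do not change the table count, and because the repeats include ALP they give more chances of a high peak.

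Three stronger readings are tempting, and the documents support none of them.
- *A case is lost.* It is not: case C remains in the parent row and changes only its sub-row.
- *Table 2-2 is the only tabulation of possible serious liver injury.* It is not. Hepatotoxicity AESI tables and listings are planned (SAP 2.7.1.1). Protocol 6.6.3.1 has confirmed cases without another cause reported as SAEs, which SAP 2.7.1 tabulates and lists.
- *The table contradicts protocol 9.1.1.* That section is a stopping criterion, not an analysis definition, and it states no upper interval. Case A fits its timing; only the bilirubin-first pattern in case B departs from it.

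Table 2-2 also does not call its low-ALP row hepatocellular. The protocol defines that pattern by R.

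**Conclusion.** The point holds in a limited form. As written, the ALP sub-rows can misclassify a genuine concurrent elevation, always by taking it out of the low-ALP row. The parent row can include pairs of unrelated peaks about 150 days apart on the nominal schedule, in either order. Both follow from the footnote itself and need no assumption.

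How often this happens does rest on assumptions. Chance pairs are expected to be rare (0.03 to 0.15 per 150 under the assumed rates and independence), and case C needs an uncommon combined event plus a separate ALP rise. The likeliest outcome is that no participant is affected. No efficacy result depends on it, and other safety outputs also cover liver injury. This is a cheap improvement to a safety table, not a flaw in the trial's safety assessment.

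**What to change.** Amend the Table 2-2 footnote and its shell before database lock:

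1. Keep the peak-based combined rows and label them as a screen built from separate peaks.
2. Add time-matched rows: ALT/AST and bilirubin criteria met in the same sample, or bilirubin met at or after the ALT/AST elevation within an interval that the SAP states. Protocol 9.1.1 gives no interval, so the SAP must choose and justify one.
3. In the time-matched rows, assign the ALP split from the ALP in the first sample of that episode that meets the ALT/AST criterion. This also settles the choice when several samples qualify.
4. List dated ALT, AST, bilirubin and ALP values for every participant in any combined row, so that a later ALP rise can be judged in context.

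Apply the same rules to the rows for participants with raised transaminases at baseline, using their own thresholds. The four parameters share one panel, so no new data are needed. The cost is a few extra table rows, a listing and minor programming.
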